#### **13.3.4 Summary of Descriptive Statistics for A4**

Descriptive statistics (11-point) for the serum A4 assessments, change from baseline in serum A4, and % change from baseline in serum A4 will be presented by scheduled time point (i.e., Baseline [serum A4 only], study Week 10, Week 14, and Week 18). Geometric means and geometric mean change from baseline, along with the associated log scale SDs will also be presented.

#### **13.3.5 Sensitivity Analyses**

The Primary Efficacy Analysis will be supported by a number of sensitivity analyses.

### 13.3.5.1 Imputation of A4 values for Missing Data

Missing data can have an adverse effect on the estimation of endpoints. As such, multiple imputation of missing data via retrieved drop-out method will be used for the primary analysis. Retrieved drop-outs are defined as subjects who prematurely discontinue study drug treatment but remain in the study and still have assessments collected at the remaining scheduled visits in the study. These subjects can provide data that is reflective of subjects who discontinue treatment early without collection of assessments. Prior to performing the MI with retrieved drop-out, all intermittent (non-monotone) missing data will be imputed assuming missing at random (MAR).

A total of 20 datasets will be stochastically imputed for each intermittent missing A4 value at Week 18 using a mixed model repeated measures (MMRM) model. In this model A4 values will be log transformed prior to analysis. The model will comprise of the log A4 values at visits 5, 6 and 7 (= study weeks 10, 14 and 18) as the dependent variable with subject as random effect; randomized treatment group (0 = placebo, 50 = 50 mg QD tildacerfont, 100 = 100 mg QD tildacerfont, and 200 = 200 mg QD tildacerfont), time (=visit), sex (0=male, 1=female), and the interaction of treatment and time as fixed effects; and the log-transformed baseline serum A4 and the baseline GC dose (in HCe) as continuous covariates in the model. Within-subject correlations will be modeled using an unstructured covariance structure. Time ordering is a repeated measure within subjects. Errors for different subjects are assumed to be independent with an unstructured covariance structure.

In the event the MMRM model with an unstructured covariance structure does not converge, the following covariance structures will be used as substitution in the order below. Each subsequent covariance structure will be used only if each previous covariance structure was used and the model did not converge.

- a) Toeplitz covariance structure (assuming measurements from samples taken closer together in time are more highly correlated than those from samples taken farther apart)

- b) First order of auto-regressive [AR(1)] covariance structure (assuming measurements from samples taken closer together in time are more highly correlated than those from samples taken farther apart)
- c) Compound symmetry covariance structure (assuming equal correlation for measurements from a subject, regardless of how far apart in time when they were taken)

Then a multiple imputation (MI) of the monotone missing data will be performed using information from retrieved dropouts, if data are available. If  $n \geq 5$  subjects in a treatment group have discontinued study drug early and have available data from which to draw values, then a retrieved dropout approach will be utilized for that treatment group using MI by fully conditional specification and predictive mean matching assuming missing not at random (MNAR).

A total of  $m$  datasets will be stochastically imputed using multiple imputation with chained equations and predictive mean matching. Multiple imputation inference involves the following three steps:

1. The non-monotone missing observations are filled in  $m$  times to generate  $m$  complete datasets using SAS® PROC MI based on the multiple imputation method.
  - a.  $m$  will be set to 20. The random seed will be set to 40
  - b. Using the Markov chain Monte Carlo method with a non-informative prior (Jeffreys) to perform a monotone-data imputation (IMPUTE=MONOTONE) by the randomized treatment group
2. Each of the resulting  $m$  imputed datasets will then be imputed again. The monotone missing observations are filled in  $m$  times to generate  $m$  complete datasets using SAS® PROC MI based on the multiple imputation method.
  - a. The random seed will be set to 50
  - b. Using the retrieved drop out subjects with complete data, predict Week 18 A4 change using a set of predictors resulting in a set of linear coefficients  $b$

$$\begin{aligned} \log(A4 \text{ postbaseline}) \\ = & \text{ Treatment} + \text{Sex} + \text{Visit} + \text{Treatment} * \text{Visit} + \log(\text{Baseline A4}) \\ & + \text{Baseline GC Dose} \\ & + \text{Last available(weeks 10 or 14)} \log(A4 \text{ postbaseline}) \end{aligned}$$

- c. Do a random draw from the *posterior predictive distribution* of  $b$  producing a new set of coefficients  $b^*$
  - d. Use  $b^*$  to generate predicted values for the Week 18 for all subjects
  - e. For each missing Week 18 A4 value, identify a set of candidates with observed Week 18 change whose predicted values are close to the predicted value for the case with missing data
  - f. From the candidates, randomly choose one Week 18 value and assign its observed value to the missing value
  - g. Repeat process for every subject with missing data
3. The analysis methods described in [Section 13.3.3](#) will be applied to the  $m$  completed datasets.

The results from the  $m$  completed datasets are combined using Rubin's rules via SAS® PROC MIANALYZE. The imputed treatment effect, 95% CI and 2-sided p-value will be presented.

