9.2 Sample Size Determination

A sample size of n=15 subjects per group will provide at least 80% power to detect a difference of at least 50% in A4 mean percent change from baseline between a given dose level of tildacerfont and placebo, assuming a common SD of 30%.

An assumed dropout rate of 15% during the Treatment Period results in a target of 18 subjects per group and a total sample size of 72 subjects who enter the Treatment Period.

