### 13.3.3 Dose Response Modeling and Testing

Statistical testing for dose response will be performed using the repeated measures random coefficients mixed-effects model described in [Section 13.3.2](#). A4 values will be log transformed prior to analysis. The model will comprise of the log A4 change from baseline through to study Week 18, i.e. though 12 weeks of double blind randomized treatment; note the actual time, in days, from baseline to each post baseline A4 value through to study week 18 will be used in this analysis. Randomized treatment group and sex will be included in the model as class factors and baseline GC dose (in HCe) as continuous covariate. Subject specific intercept, time (in days)

and time x time random effects will be included. Further, randomized treatment by time and randomized treatment by time x time interactions will be included. The model will be fitted using maximum likelihood estimation. If the variance component for time or time x time are estimated to be zero then the corresponding term (or terms) will be retained in the model as fixed effects and the analysis re-run.

To test the union intersection hypothesis  $H_{0L} \cap H_{QL}$ , the model will be fitted with and without the randomized treatment by time and randomized treatment by time squared interactions terms. The difference in -2 log likelihood between models will be compared to the  $\chi^2_{df}$  cumulative distribution function on the appropriate degrees of freedom (i.e.  $df = 6$ ), this will provide the p-value to determine if the union intersection hypothesis can be rejected at the 10% alpha level; if so then there is evidence for a treatment effect of tildercerfont over placebo.

The fitted A4 change from baseline versus time profile will be extracted from the model for each randomized treatment and displayed graphically, superimposed upon the A4 time profiles for individual subjects.

Note, the programming of the repeated measures random coefficients mixed-effects model is particularly complex, hence example SAS codes perform the analysis are presented in Appendix D.

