#### **13.4.1.2 Supportive MMRM Tipping Point Analysis**

A supportive MMRM sensitivity analysis using the tipping-point approach will be conducted. Tipping point MI analysis is a method to explore the influence of missingness on statistical inference by imputing the missing data in the drug arm with an increasing degree of penalization (shift parameter). The analysis finds a (tipping) point in this wider range of imputed values, at which conclusions change from being favorable to the experimental treatment to being unfavorable. After such a tipping point is determined, clinical judgment can be applied as to the plausibility of the assumptions underlying this tipping point. Tipping point MI is performed as follows:

1. Repeat MI Step 1 as described in [Section 13.3.5.1](#) to generate multiple imputed data sets, with a specified shift parameter that adjusts the imputed values for observations in the treatment group, not the placebo group.
2. Repeat MI Step 2 for the imputed data sets with shift parameter applied.
3. Repeat MI Step 3 to obtain the p-value to see if the p-value is still  $\leq 0.05$ .
4. Repeat steps 1-3 with a more stringent shift parameter applied until the p-value  $> 0.05$ .

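### The A4 imputation chain names no poolable quantity, leaves its donor pool and fallback unsettled, and on a literal reading its tipping point never shifts a missing Week 18 value

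*SAP*

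**What the plan says.** **Role.** SAP 13.3.5.1 states that "multiple imputation of missing data via retrieved drop-out method will be used for the primary analysis". The same text sits under 13.3.5, Sensitivity Analyses, and Protocol 9.4.2 makes a missing-data sensitivity analysis optional. Protocol 9.4.1 and SAP 10.2.1 describe retrieved-dropout imputation as the general approach.

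**Test and pooling.** SAP 13.3.3 fits the random-coefficients model by maximum likelihood with and without the treatment-by-time and treatment-by-time-squared terms: "The difference in -2 log likelihood between models will be compared to the" chi-square distribution on 6 df, at a 10% level. Step 3 of 13.3.5.1 applies 13.3.3 to the imputed datasets, combines them in PROC MIANALYZE, and concludes: "The imputed treatment effect, 95% CI and 2-sided p-value will be presented".

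**Donors.** Step 2b fits the imputation regression on retrieved dropouts. Step 2d predicts for all subjects. Step 2e is to "identify a set of candidates with observed Week 18 change whose predicted values are close" to the prediction for the missing case, and 2f draws one of them.

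**Trigger and fallback.** SAP 10.2.1 treats 5 or fewer per group as insufficient and sends the reader to Section 13.4. SAP 13.3.5.1 treats 5 or more as sufficient.

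**Tipping point.** SAP 13.4.1.2 repeats MI Step 1 "with a specified shift parameter that adjusts the imputed values for observations in the treatment group, not the placebo group", then repeats Steps 2 and 3, and increases the shift until p exceeds 0.05.

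**The concern.** The chain breaks at three places.

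1. Rubin's rules combine estimates and their variances. A likelihood-ratio statistic supplies neither. The programmer must therefore choose a quantity to pool, or invent a way to pool the test, after the SAP is final.
2. A retrieved-dropout method represents people off drug by other people off drug. If step 2e admits anyone with an observed Week 18 value, subjects off drug can receive values from subjects still on treatment. The trigger, the missingness labels and the fallback also conflict, so it is unclear which method applies to a given arm.
3. The tipping point should penalise the values most in doubt, which are Week 18 values after dropout in the active arms. A shift confined to MI Step 1 would miss them, and the analysis would look robust without having tested anything.

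At stake is prespecification. SAP Section 4 says the methods are fixed before lock and unblinding, and these are not.

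**Working it through.** **Plan figures reproduced**

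- Protocol 9.2: "An assumed dropout rate of 15% during the Treatment Period results in a target of 18 subjects per group". 15 / (1 - 0.15) = 17.6, rounded up to 18; 4 x 18 = 72. This agrees.
- SAP 13.3.3: 3 doses x 2 interaction terms = 6 df. This agrees. Critical values are 10.64 at 10% and 12.59 at 5%.

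**Pooling**

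The pooled output is to be an effect, an interval and a p-value. Section 13.4.1 takes dose-versus-placebo differences with intervals and p-values at 4, 8 and 12 weeks from this same model. Those are scalars and can be pooled, but step 3 cites 13.3.3 and names no contrast.

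To see whether the choice of rule matters for the 6-df test, two rules were simulated under the null (20 imputations, nominal 10%; fractions of missing information are assumed):

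| Fraction of missing information | Average of the 20 LR statistics vs chi-square 6 df | Multivariate Wald pool |
|---|---|---|
| 5% | 13% | 10% |
| 10% | 18% | 10% |
| 15% | 23% | 10% |
| 30% | 46% | 10% |

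The SAP does not propose averaging. The table shows why a rule has to be written down.

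**How often the retrieved-dropout step would run**

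Assume that 15% is the rate of stopping drug by Week 18 and that a share s of those subjects is retrieved. The number retrieved per arm is then Binomial(18, 0.15 x s).

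- s = 1: expected 18 x 0.15 = 2.7; P(5 or more) = 12.1%
- s = 1/2: expected 1.35; P = 0.9%
- s = 1/4: expected 0.675; P = 0.04%

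The chance that at least one of four arms qualifies is 40% at s = 1 and 3.5% at s = 1/2. At s = 1, however, every dropout has data and nothing is left for the step to impute. With a 25% stopping rate the per-arm figures are 48% (s = 1) and 6.5% (s = 1/2).

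The 15% in Protocol 9.2 covers the 70-week Treatment Period. Under a constant hazard, 12 weeks gives 1 - 0.85^(12/70) = 2.7%, or about 0.5 per arm, and P(5 or more) is then about 0.01%. For most arms the fallback is the route.

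**Trigger and fallback side by side**

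- At exactly 5, SAP 10.2.1 uses the fallback and 13.3.5.1 uses retrieved dropouts.
- SAP 10.2.1 labels the retrieved-dropout method missing at random and the fallback missing not at random. SAP 13.3.5.1 labels the retrieved-dropout step missing not at random.
- The only imputation method within 13.4 is the tipping point in 13.4.1.2, whose steps refer back to 13.3.5.1.

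**Where the shift lands**

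The imputation model holds Weeks 10, 14 and 18. A gap is intermittent only if a later value in the model is observed, so a missing Week 18 value, being last, is monotone. MI Step 1 fills only non-monotone gaps, and Step 2 fills Week 18. A shift in Step 1 therefore reaches only Weeks 10 and 14. (SAP 13.3.5.1 does mention an intermittent gap at Week 18, which this three-visit model cannot contain.)

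Illustration (assumed: 18 per arm, two arms, 15% monotone dropout, log SD 0.6, correlation 0.7, true Week 18 effect log 0.6 = -0.51; simple difference in means, 150 simulated trials per setting):

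| Intermittent gaps | Shift in Step 1, 0 to 2 log units | Shift on monotone Week 18 values, 0 to 2 |
|---|---|---|
| 0% | -0.50 to -0.50 | -0.50 to -0.22 |
| 5% | -0.49 to -0.49 | -0.49 to -0.20 |
| 15% | -0.52 to -0.52 | -0.52 to -0.23 |

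With no intermittent gaps, the share of trials significant in favour of drug stayed at 72% under the Step 1 shift and fell from 72% to 17% under the Week 18 shift. A loop that waits for p to exceed 0.05 may never stop under the first. The tipping point's Step 3 also leads to the 13.3.3 likelihood-ratio test, judged at 10%, although its title promises an MMRM.

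**The case against.** The best reply is that the intent can be recovered throughout, and much of that stands.

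- **A reader might infer that the trial has no primary p-value.** The documents do not support this. SAP 13.3.3 specifies a maximum-likelihood test that runs on observed data without imputation. The defect is that the imputation is both called primary and filed as a sensitivity analysis.
- **The pooled effect has a natural meaning.** The contrasts in 13.4.1 and the Week 18 forest plot in 13.3.5.3 come from the same model and pool validly. That holds, but step 3 must say so.
- **A reader might infer that dropouts would mostly receive on-treatment values, to the drug's advantage.** SAP 10.2.1 and the sentence introducing step 2 both point to retrieved dropouts as the data source, so this is an internal conflict and not a decision to use everyone. Predictive mean matching draws from the nearest predictions, so the make-up of the pool does not give the chance of selection.
- **A reader might infer zero residual df at n=5, or 400 datasets.** The first needs a separate five-coefficient fit per arm, but the printed equation contains treatment and suggests a fit across arms. The second takes one loose phrase against repeated statements that there are m datasets.
- **A reader might say the tipping point certainly spares dropouts.** Its stated aim is to penalise missing drug-arm data in general, and its second line can be read as shifting Step 2 too. The literal reading is the natural one, not the only one. It is a supportive analysis of a secondary endpoint tested without alpha control.

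**Conclusion.** The concern holds as a specification failure. As written, the chain does not deliver the pooled result it promises: the effect is unnamed, the 6-df test has no pooling rule, step 2e lacks the donor restriction stated elsewhere, the trigger and labels conflict, the likely fallback is not described, and the shift literally misses Week 18. An observed-data primary p-value remains available, and the size and direction of any bias from the donor rule are not established.

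The 12% figure assumes that 15% stop drug by Week 18 and that all are retrieved, which is generous to the retrieved-dropout route at that rate. The rejection rates and tipping-point figures rest on assumed missing information, SD, correlation and effect. They show that the choices matter, not what this trial would find. This should be fixed before lock and unblinding. It does not invalidate the design.

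**What to change.** - State whether the observed-data or the imputed analysis is primary.
- In step 3, name the pooled estimand: the log-scale difference of each dose versus placebo at Week 18 (12 weeks of treatment), combined by Rubin's rules.
- If the 6-df test is also to be reported after imputation, pool the six interaction coefficients and their covariance with the multivariate TEST in PROC MIANALYZE, or use a Meng-Rubin pooled likelihood-ratio test.
- In step 2e, restrict donors to retrieved dropouts. State that the regression is fitted across arms with treatment as a covariate.
- Make the n=5 trigger and the missingness labels agree between 10.2.1 and 13.3.5.1, and write out the fallback where 10.2.1 refers to it.
- Use one Step 2 imputation per Step 1 dataset.
- In 13.4.1.2, add the shift to the imputed monotone Week 18 values in the active arms, and take the p-value from the pooled MMRM contrast of 200 mg versus placebo.

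The cost is SAP wording and code, with no new data. The imputed result may come out slightly less favourable.

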### 13.3.5.2 Per-Protocol Analysis and mITT Sets

The primary analysis of A4 as described in [Section 13.3.3](#) will be repeated in the PP and mITT Analysis Sets ([Section 8.3](#)) as supportive analyses.

### 13.3.5.3 Subgroup Analyses

The primary analysis of A4 as described in [Section 13.3.3](#) repeated for each subgroup specified in [Section 10.7](#) for the ITT Analysis Set. A forest plot of the estimated treatment effects at Week 18 by dose level and subgroups will be provided.

### 13.3.5.4 Handling A4 Assessments Collected During GC Stress Dosing

## 13.4 Secondary Efficacy Analyses

The analysis population for Secondary Efficacy Analyses is the ITT analysis set, including all classic CAH subjects who were randomized into the study.

### 13.4.1 First Secondary Efficacy Analysis

The First Secondary Efficacy Analysis (see [Table 1](#), Analysis 2.1) relates to the change from baseline in A4 as assessed on the log scale after 12 weeks on double-blind, placebo-controlled treatment. This analysis will be achieved as an integral part of the dose response modelling as described in [Section 13.3.3](#).

The estimated mean change from baseline in log A4 values at 4, 8 and 12 weeks of double blind randomized treatment will be extracted from the model by treatment arm as will the difference and associated 95% CI and p-value between each tildacerfont dose and placebo at each of 4, 8 and 12 weeks. To facilitate ease of interpretation, the estimated mean change from baseline in log A4 for each tildacerfont dose and placebo will be back transformed resulting in the estimated ratio of geometric means to baseline, i.e. the back transformed log scale estimated mean change becomes  $\{\text{estimated A4 geometric mean at time } x\}/\{\text{estimated A4 geometric mean at baseline}\}$  = GMR. Hence, GMR – 1 becomes the percentage CFB in geometric means. Further, the difference between each tildacerfont dose and placebo in estimated mean change from baseline in log A4 (along with the associated 95% CI) will also back transformed resulting in the ratio of  $\{\text{A4 GMR tilda at time } x\}/\{\text{A4 GMR placebo at time } x\}$  as the measure of treatment effect. And, again,  $\{\text{A4 GMR tilda at time } x\}/\{\text{A4 GMR placebo at time } x\} - 1$  becomes the percentage reduction (or increase) in geometric mean A4 values at time  $x$  for tildacerfont compared to placebo.

In addition orthogonal linear and quadratic contrasts between treatments at 12 weeks of double blind randomized treatment will also be estimated as a supportive measure of dose response at this time point.

Example SAS codes in relation to the First Secondary Efficacy Analysis are provided in Appendix D.

A serial plot will be presented of the estimated mean change from baseline in log A4 over time. The y-axis will be the percent CFB (i.e  $100 \{ \exp(\text{estimated change from baseline in log A4}) - 1 \}$ ) and the x-axis will represent the Part A visits, baseline, Week 4, Week 8, and Week 12 of double blind randomized treatment. All treatment groups will be presented on the graph.

#### **13.4.1.1 Supportive MMRM Analysis**

A supportive analysis of the log change from baseline in A4 will be achieved via conventional MMRM modelling as described in [Section 13.3.5.1](#). The log scale change from baseline (CFB) least squares (LS) means will be extracted from the model for each tildacerfont dose and placebo at study Weeks 10, 14 and 18, along with the associated SEs and 95% CIs. Further, the treatment effect for each tildacerfont dose versus placebo, being the corresponding difference in log scale LS means, will also be extracted along with the associated SE, 95% CI and 2-sided p-values.

To facilitate ease of interpretation, LS means, differences in LS means and associated 95% Cis s will be back transformed in the same fashion described in [Section 13.4.1](#).

#### **13.4.1.2 Supportive MMRM Tipping Point Analysis**

A supportive MMRM sensitivity analysis using the tipping-point approach will be conducted. Tipping point MI analysis is a method to explore the influence of missingness on statistical inference by imputing the missing data in the drug arm with an increasing degree of penalization (shift parameter). The analysis finds a (tipping) point in this wider range of imputed values, at which conclusions change from being favorable to the experimental treatment to being unfavorable. After such a tipping point is determined, clinical judgment can be applied as to the plausibility of the assumptions underlying this tipping point. Tipping point MI is performed as follows:

1. Repeat MI Step 1 as described in [Section 13.3.5.1](#) to generate multiple imputed data sets, with a specified shift parameter that adjusts the imputed values for observations in the treatment group, not the placebo group.
2. Repeat MI Step 2 for the imputed data sets with shift parameter applied.
3. Repeat MI Step 3 to obtain the p-value to see if the p-value is still  $\leq 0.05$ .
4. Repeat steps 1-3 with a more stringent shift parameter applied until the p-value  $> 0.05$ .

